6.3.3 Up-dosing Period

The Up-dosing Period will last approximately 20 (to a maximum of 40) weeks and comprise 10 scheduled Up-dosing Visits (including the first 300 mg dose of the Maintenance Period), with the potential for Unscheduled Visits for assessment of dose tolerability, dose-reduction, dose re-escalation, or management of AEs.

Subjects will return to the clinic every 2 weeks for up-dosing to a maximum daily dose of 300 mg. The first dose of IP at each new dose level will be administered in the CRC under direct observation and medical supervision.

Subjects must be free from active wheezing, a flare of atopic disease (eg, atopic dermatitis), or suspected intercurrent illness prior to any dose escalation. Subjects should be maintained on their current, or a reduced, dose level of IP until their flare of asthma, atopic disease, or intercurrent illness has resolved.

Subjects should withhold their daily home dose of IP on in-clinic dosing days, but should take all other prescribed medications as scheduled.

6.3.3.1 Up-dosing Visits

The following assessments/procedures are scheduled for each Up-dosing Visit in the CRC:

- Concomitant medication review
- Contraception review
- Diet (food allergen exposure) history update
- Return unused IP
- Symptom-directed physical examination
- Pre-dose vital sign measurement (BP, pulse rate, body temperature)
- PEFR (3 attempts are to be performed, and the best value taken). PEFR should be measured at the same time of day for each visit assessment (eg, morning, afternoon, evening)
- IP administration under observation in the clinic
- Post-dose vital sign measurements (BP, pulse rate) at the following times:
 - Within 15 to 30 minutes post-dose,
 - At 30-minute intervals thereafter, if the time between doses is extended, and for the duration of the post-dose observation period.
- Provide subject with IP for daily dosing until next visit
- Monitoring for dosing compliance
- Monitoring for AEs, including allergic symptoms (below and [Section 6.7](#) and [Section 7.2](#)) and review of symptoms reported in subject diary
- Subjects will be reminded to continue to follow a peanut-avoidant diet for the duration of the study.

At a minimum, subjects must be observed for 90 minutes after dose administration, with vital sign measurements and assessment for signs and symptoms of allergic reaction performed every 30 minutes. Any signs or symptoms of allergic reaction will be recorded in the CRF on the appropriate Dosing Symptom/AE form.

- If up-dosing is completed with no symptoms detected after 90 minutes of post-dose observation, the subject may be sent home from the CRC.
- If the subject exhibited **mild symptoms**, the duration of the observation period should be extended beyond 90 minutes, if applicable, so that the subject is observed for a minimum of 1 hour after resolution of the symptoms.
- For **moderate symptoms**, the observation period should be extended to a minimum of 2 hours after resolution of the symptoms.
- For **severe symptoms**, the subject should be observed for a minimum of 3 hours after resolution of the symptoms, either at the CRC or an emergency facility, as appropriate.

- Any subject deemed to have **severe symptoms** that include hypoxia, hypotension, or change in mental status (stage 3 anaphylaxis defined in [Appendix 3](#)), or who receives intensive therapy (to be determined by the investigator, but may include such interventions as IV epinephrine, intubation, or admission to an intensive care unit) for an allergic reaction at any time should be discussed with the medical monitor and discontinued from the study.
- On the day following in-clinic up-dosing, the site is to make telephone contact with the subject/subject's parent or guardian to enquire if any AEs (including allergic symptoms) occurred subsequent to the subject leaving the clinic, and to provide assistance in the recording of any such events in the diary.
- A dose escalation attempt may be postponed 1 to 2 weeks if, in the clinical judgment of the investigator, the current dose level has not been sufficiently well tolerated to proceed to the next dose level.
- If an investigator suspects that a subject has not tolerated, or is not tolerating, his or her current dose level, the investigator should have the subject return to the clinic to determine whether a dose reduction is warranted, and if so, the magnitude of the reduction. The investigator may also decide to maintain the current dose or to withhold dosing. Guidelines for setting the new, lower dose are outlined in [Section 6.7.5](#), with the dose adjustment depending on the severity of the dose-related symptoms.
- Subjects who require dose reduction during a 2-week dosing period will have their escalation schedule reset, as necessary, to maintain the new dose level for a 2-week period prior to attempting to re-escalate.
- Following a dose reduction, it is advised that an escalation attempt be made by 4 weeks, unless escalation is to be delayed further due to administration of epinephrine, as defined in [Section 6.7](#). Failure to successfully escalate after 3 consecutive attempts, with each attempt spaced at least 2 weeks apart, will result in the cessation of dosing. The subject will be asked to return to the CRC 14 to 16 days following the last dose of IP to undergo an Early Discontinuation Visit ([Section 6.4](#)) and is to be followed for safety in the interim.
- For symptoms occurring during the Maintenance Period, the same study dosing rules and guidelines that apply for the Up-dosing Period will also apply.

6.3.3.2 80 mg Up-dosing Visit

The 80 mg Up-dosing Visit is the approximate midpoint of the Up-dosing Period. At the 80 mg Up-dosing Visit the following procedures are to be performed in addition to those performed at the other Up-dosing Visits:

- Complete physical examination, including height and weight
- In subjects with asthma: evaluation of asthma severity using the 2007 NHLBI Criteria ([Appendix 2](#)) and the Asthma Control Test questionnaire
- Urine pregnancy test for females of childbearing potential

- Review home dosing instructions
- Review with subjects and parents or guardians teaching about food/peanut allergy according to the investigational site's established standards. This is to include at a minimum the following topics (some or all of which may be addressed in a comprehensive anaphylaxis action plan):
 - Recognition of an allergic reaction and of the symptoms of anaphylaxis
 - When and how to administer epinephrine via auto-injector
 - Requirement to go to nearest emergency facility following use of epinephrine auto-injector
 - Ways to minimize the risk of accidental exposure to peanut in, and outside of, the home (may be supplemented by referral to recognized food allergy organizations for access to additional learning materials)

6.3.3.3 300 mg Up-dosing Visit

At this visit the following procedures are to be performed in addition to those performed at the Up-dosing Visits:

- Complete physical examination, including height and weight
- In subjects with asthma: evaluation of asthma severity using the 2007 NHLBI Criteria ([Appendix 2](#)) and the Asthma Control Test questionnaire
- Urine pregnancy test for females of childbearing potential
- Blood draw (same venipuncture for all samples) to collect samples for:
 - Peanut- and peanut component-specific IgE, total IgE, and peanut-specific IgG4 assays
 - CBC
 - Optional blood sample for immune cell characterization assays

The amount of blood to be taken in total for all tests (required immunoglobulin and CBC and optional immune cell characterization assays) will be included in the manual of procedures and will not exceed a total volume of 2.5 mL/kg, to a maximum total of 70 mL on any study day. Blood draw should be collected in compliance with local laboratory guidelines and testing regulations. Multiple attempts to obtain blood, and repeat samples can be collected where necessary for damaged samples or safety reasons.

- SPT to peanut extract
- Review home dosing instructions
- Review with subjects and parents or guardians teaching about food/peanut allergy according to the investigational site's established standards. This is to include at a minimum the following topics (some or all of which may be addressed in a comprehensive anaphylaxis action plan):

- Recognition of an allergic reaction and of the symptoms of anaphylaxis
- When and how to administer epinephrine via auto-injector
- Requirement to go to nearest emergency facility following use of epinephrine auto-injector
- Ways to minimize the risk of accidental exposure to peanut in, and outside of, the home (may be supplemented by referral to recognized food allergy organizations for access to additional learning materials)

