6.7 Assessment and Treatment of Allergic Reactions to Peanut OIT

6.7.1 Assessment of the Severity of Acute Allergic Reactions to Peanut OIT

Subjects may develop allergic symptoms during the course of OIT, similar to those that may occur during other desensitization protocols (eg, venom immunotherapy, drug desensitization, desensitization to aeroallergens by subcutaneous injection). The severity of the reaction will be determined on the basis of the investigator's judgment. The following definitions, developed to be consistent both with the PRACTALL consensus report on DBPCFC and with the CoFAR grading system for allergic reactions, are provided as a general guide.

Mild symptoms:

- Skin – limited (few) or localized hives, swelling (eg, mild lip edema), skin flushing (eg, few areas of faint erythema), or pruritus (eg, causing mild occasional scratching)
- Respiratory – rhinorrhea (eg, occasional sniffling or sneezing), nasal congestion, occasional cough, throat discomfort
- GI – mild abdominal discomfort (including mild nausea), minor vomiting (typically a single episode), and/or a single episode of diarrhea

Moderate symptoms:

- Skin – systemic hives (eg, numerous or widespread hives), swelling (eg, significant lip or face edema), pruritus causing protracted scratching, more than a few areas of erythema, or pronounced erythema
- Respiratory – throat tightness without hoarseness, persistent cough, wheezing without dyspnea
- GI – persistent moderate abdominal pain/cramping/nausea, more than a single episode of vomiting and/or diarrhea

Severe symptoms:

- Skin – severe generalized urticaria/angioedema/erythema
- Respiratory – laryngeal edema, throat tightness with hoarseness, wheezing with dyspnea, stridor
- GI – severe abdominal pain/cramping/repetitive vomiting and/or diarrhea
- Neurological – change in mental status
- Circulatory – clinically significant hypotension ([Appendix 3](#))

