Based on experience from Phase 2 studies, most acute allergic responses to dosing that are characterized by mild symptoms would be anticipated to meet the above criteria. If, however, an allergic response to dosing is characterized by mild symptoms that do not meet all of the above criteria (eg, has mild symptoms occurring in 2 or more organ systems, requires treatment with 2 doses of antihistamine or 1 dose epinephrine, shows progression in severity or distribution over time, is protracted in duration, or includes objective wheezing), then even though the allergic symptoms may be mild, the dose should be assessed as not tolerated. If a dose elicits mild symptoms that do not fit all of the above criteria and the dose is assessed to

be tolerated, then a brief explanation as to why the dose was considered tolerated must be recorded in the CRF.

Moderate symptoms: In general, if a dose elicits moderate symptoms, the dose will be assessed as not tolerated. However, there may be rare occasions when a dose eliciting moderate symptoms could be assessed as tolerated. This would only be the case for a transient, self-limited (requiring no intervention and resolving completely) symptom occurring in a single organ system. In addition, the symptom would be typically subjective only. Any dose associated with moderate symptoms and assessed as tolerated must be accompanied by a brief explanation in the CRF as to why the dose was considered tolerated.

Severe symptoms: In nearly all cases, if a dose elicits severe symptoms, the dose will be assessed as not tolerated. Whenever a dose elicits an allergic response characterized by 1 or more severe symptoms, the crucial decision, after adequate treatment for the allergic reaction has been administered, will be to determine whether the subject should continue in the study, dosing at a reduced dose level, or be discontinued early from the study.

The determination of tolerability will decide the course of action to be taken in response to dose-related reactions ([Section 6.7.3](#)).

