level for an additional 2 weeks. If the subject experiences mild symptoms at the reduced dose, the procedures for responding to a dose with mild symptoms should be followed (above and [Figure 3](#)). If the subject experiences moderate symptoms at the reduced dose level, the subject should return to the CRC the next day and receive a further 1- or 2-step dose reduction (per investigator judgment). If this reduced dose is well tolerated, it will be continued as the daily home dose for at least 2 weeks before re-escalation is attempted in the CRC. If the dose is not well tolerated, but elicits mild symptoms, then the treatment procedures for responding to mild symptoms should be followed (above and [Figure 3](#)). If, however, the subject again experiences moderate symptoms at the reduced dose level, a discussion with the medical monitor is to ensue to reach a decision as to whether to continue the subject in the study.

In the rare instance that a dose eliciting moderate symptom is *assessed as tolerated*, then the actions taken should be the same as for a dose with mild symptoms *assessed as tolerated*.

- **Severe symptoms:** If *severe symptoms* occur, the action should be to treat the subject for the allergic reaction, and then, in consultation with the medical monitor, decide whether or not to discontinue the subject from the study. If it is determined that it is safe to allow the subject to continue in the study, the subject should return to the CRC the next day for dosing at a 2-step reduction in dose under observation. If the subject tolerates the dose reduction (ie, shows no or only mild symptoms that are assessed as tolerated), then the subject is to remain at the reduced dose level for at least 2 weeks before returning to the CRC to attempt dose re-escalation. If the subject does not tolerate the reduced dose, then the subject is to be considered an escalation failure non-responder.

Consult the medical monitor for specific questions related to dose escalation or continuation of the same dose that are not answered in the procedures described above.

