Appendix 4: Allergic Reaction Severity Grading

The CoFAR grading system for allergic reactions is displayed in [Table A4](#).

Table A4: CoFAR Specific Grading System for Allergic Reactions

Grade 1 – Mild	Grade 2 – Moderate	Grade 3 – Severe	Grade 4 – Life Threatening	Grade 5 – Death
Transient or mild discomforts (< 48 hours), no or minimal medical intervention/therapy required. These symptoms may include pruritus, swelling or rash, abdominal discomfort, or other transient symptoms.	Symptoms that produce mild to moderate limitation in activity, some assistance may be needed; no or minimal intervention/therapy is required. Hospitalization is possible. These symptoms may include persistent hives, wheezing without dyspnea, abdominal discomfort/increased vomiting, or other symptoms.	Marked limitation in activity, some assistance usually required; medical intervention/therapy required, hospitalization is possible. Symptoms may include bronchospasm with dyspnea, severe abdominal pain, throat tightness with hoarseness, transient hypotension among others. Parenteral medication(s) are usually indicated.	Extreme limitation in activity, significant assistance required; significant medical intervention/therapy is required. Hospitalization is probable. Symptoms may include persistent hypotension and/or hypoxia with resultant decreased level of consciousness associated with collapse and/or incontinence or other life-threatening symptoms.	Death

Appendix 5: Guidance for Determining When an Episode of Anaphylaxis Should Be Reported as a Serious Adverse Event (SAE)

For an episode of anaphylaxis to be considered an SAE, the sponsor advises that the event satisfy 1 of the outcome-based definitions of SAE specified in [Section 7.3.1.1](#), with the stipulations (denoted in *italics*) indicated. These stipulations follow from, and are consistent with, the criteria for DSMC reporting ([Section 7.9.3](#)):

1. Death – *No further stipulation.*
2. Life-threatening AE (life-threatening means that the study subject was, in the opinion of the investigator or sponsor, at immediate risk of death from the reaction as it occurred):
For anaphylaxis to be considered life-threatening it should be assessed to have been severe, as defined in [Appendix 3](#) and of a Grade 4 allergic reaction, as defined in [Table A4](#) of [Appendix 4](#).

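### Section 6.3.3.1 calls for discontinuation after stage 3 reactions, but Sections 6.7.2 and 6.7.5.1 leave continuation open for all severe reactions, and Section 4.3.1 does not fully close the gap

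*Protocol*

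**What the plan says.** Section 6.3.3.1 (Up-dosing Visits) singles out a subset of severe reactions: those "that include hypoxia, hypotension, or change in mental status", which it equates with stage 3 anaphylaxis in Appendix 3, and any reaction for which intensive therapy is given. A subject treated "for an allergic reaction at any time should be discussed with the medical monitor and discontinued from the study" is the stated outcome, and the sentence offers no route to continue. Sections 6.3.3.1, 6.3.4 and 6.7.7 carry the up-dosing rules into Maintenance.

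Section 6.7.1 lists, within its ordinary severe category, "Neurological – change in mental status" and "Circulatory – clinically significant hypotension".

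Section 6.7.2 then says that, whenever a dose produces one or more severe symptoms, the key decision after treatment is "to determine whether the subject should continue in the study, dosing at a reduced dose level, or be discontinued early from the study". Section 6.7.5.1 says the site should treat a severe reaction and then, "in consultation with the medical monitor, decide whether or not to discontinue the subject from the study". If continuing is judged safe, the subject returns the next day for an observed dose two steps lower. Neither section excepts the Section 6.3.3.1 events or refers to Section 6.3.3.1 or 4.3.1.

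Section 4.3.1 is the general termination list. Item 1 covers life-threatening symptoms, labelled CoFAR Grade 4, and gives anaphylaxis with hypotension or neurological compromise among its examples. Item 2 covers Grade 3 symptoms that need intensive therapy or recur. It lets other severe reactions continue if they show no sign of a serious clinical condition and both the investigator and the medical monitor agree. Table A4 in Appendix 4 gives as Grade 3 examples "throat tightness with hoarseness, transient hypotension among others".

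**The concern.** The sections overlap on the same reactions but differ in kind: one states an outcome, while the others state a decision whose result may be either outcome. If the specific rule is meant to override the general procedure, the protocol does not say so at the place where a site would look up what to do after a severe reaction.

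Two things depend on the answer. The first is whether a child who has just had a stage 3 reaction may be given investigational product again, possibly the next day. The second is the primary outcome. Under Section 9.2.1, anyone who stops oral immunotherapy before the Exit DBPCFC is a treatment failure, whereas a subject who continues may still become a responder. If sites apply different sections to the same event, they handle participants differently and may assign different responder status.

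**Working it through.** No formula decides this point, so the passages are applied to specific reactions.

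**Two scales are in use.** Section 6.3.3.1 uses the Appendix 3 stages, where stage 3 is hypoxia, hypotension or neurological compromise, including SpO2 at or below 92%. Section 4.3.1 uses CoFAR grades. In Table A4, Grade 4 is illustrated by persistent hypotension and/or hypoxia that lowers consciousness, and transient hypotension belongs to Grade 3. A reaction can therefore be stage 3 without being Grade 4.

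**Case A: one episode of transient hypotension, no intensive therapy, no recurrence.**

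| Section | Result |
|---|---|
| 6.3.3.1 | Discontinue |
| 4.3.1 item 1 | Unclear: hypotension is an example, but the Grade 4 label does not fit |
| 4.3.1 item 2 | Termination not triggered; continuation depends on whether this counts as a sign of a serious clinical condition, which is not defined |
| 6.7.2 | A decision: continue at a reduced dose or discontinue |
| 6.7.5.1 | A decision with the medical monitor; next-day reduced dosing if judged safe |

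**Case B: SpO2 at or below 92% without reduced consciousness, intensive therapy or recurrence.** This is stage 3, so Section 6.3.3.1 says discontinue. It does not match the Grade 4 illustration in Table A4. Section 6.7.1 does not name hypoxia, but Section 6.3.3.1 itself treats such a reaction as severe. Once it is graded severe, Sections 6.7.2 and 6.7.5.1 apply as in Case A.

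**Case C: a reaction with neurological compromise.** Item 1 of Section 4.3.1 names this feature, so that section largely agrees with Section 6.3.3.1. What is missing is an exception or cross-reference in Sections 6.7.2 and 6.7.5.1.

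**Case D: a severe reaction given intensive therapy.** Item 2 of Section 4.3.1 and Section 6.3.3.1 agree on termination. Again only the cross-reference is missing.

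The firm conflict is therefore Cases A and B.

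**Size.** The documents give no rate for Cases A and B. Section 9.4 plans 120 AR101 subjects, so one subject changing status moves the AR101 response rate by 1/120 = 0.83 percentage points. As an illustration only, four subjects all changing status would move it by 4/120 = 3.3 points. The difference for which Section 9.4 claims at least 80% power is 39% - 15% = 24 points.

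**The case against.** The strongest reply is that the sections can be followed together. Section 4.3.1, to which Section 7.11.2 refers for further individual stopping rules, names hypotension and neurological compromise, terminates for intensive therapy, and restricts continuation to severe reactions without serious features. Section 6.7.5 adds that the investigator must discontinue a subject whose health could be jeopardized. Section 6.7.5.1 does not order redosing: it requires consultation with the medical monitor and a finding that continuing is safe. On this view the specific stopping rule simply narrows the general procedure, and the monitor limits divergence between sites.

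Much of this stands. A reader might infer that, for every stage 3 reaction, one page commands withdrawal and another commands redosing. The documents do not support that, because redosing is only permitted and Section 4.3.1 largely agrees with Section 6.3.3.1.

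The reply does not dispose of Cases A and B. A site can satisfy all the sections by always discontinuing. A site that consults the monitor, judges continuation safe and redoses has followed Section 6.7.5.1 and departed from Section 6.3.3.1. That the specific rule prevails is an inference the protocol never states. The monitor does not remove the problem either, since the monitor works from the same text.

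**Conclusion.** The protocol is inconsistent as written, over a limited range. The overlap in wording covers all the Section 6.3.3.1 events, but the conflict that Section 4.3.1 leaves open is chiefly a non-recurrent stage 3 reaction that is not clearly Grade 4 and receives no intensive therapy. For that reaction a site could discontinue under one section or permissibly continue under another.

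A reader might also multiply the figure of under 1% with severe symptoms in Section 1.6, or the one of 29 AR101 subjects in ARC001 with a treatment-related anaphylactic SAE, by 120 and conclude that about 1 to 4 children are affected. The documents do not support that count. The first figure covers all severe symptoms, and the ARC001 event is not described as stage 3. The number affected is unknown, and the effect on the primary result is likely small at 0.83 points per subject. The case for correction rests on participant safety and uniform conduct.

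This reading relies on the text alone, because the dose-adjustment schematic (Figure 3) is not shown. It takes no view on which clinical rule is right.

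**What to change.** Reconcile Sections 6.3.3.1, 6.7.2, 6.7.5.1 and 4.3.1 into one rule for reactions with hypoxia, hypotension, altered mental status or intensive therapy. Define those reactions on one severity scale, either the Appendix 3 stage or the CoFAR grade, so that transient hypotension and low SpO2 without reduced consciousness fall clearly on one side. Cross-refer to that rule wherever the severe-symptom decision is described, and check Figure 3 against it. The sponsor's clinical team decides which rule stands.

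The cost is wording in four sections, with the approvals that Section 11.1 requires for any amendment. No participants, visits or analyses are added.
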